# Secondary outcome measure

- 1) Quality of Life Questionnaire
- 2) Measure of Anxiety and Depression
- 3) Muscle strength
- 4) Borg dyspnoea score

#### 4. PARTICIPANT ENTRY

#### 4.1 PRE-REGISTRATION EVALUATIONS

6 Minute Walk Test as part of ambulatory oxygen assessment

#### 4.2 INCLUSION CRITERIA

- 1) A confirmed diagnosis of Chronic Obstructive Pulmonary Disease (COPD)
- 2) Fulfil the clinical criteria for Pulmonary Rehabilitation (PR)
- 3) Demonstrate exercise-induced desaturation (defined as a fall in  $SaO_2 \ge 4\%$  to at least <90%, or any fall to a  $SaO_2 < 90\%$ ) and demonstrate positive improvement with use of ambulatory oxygen as per the British Thoracic Society 2015 Oxygen Guidelines

#### 4.3 EXCLUSION CRITERIA

- 1) Use of long term oxygen therapy
- 2) Unable to provide informed consent
- 3) Significant respiratory disease other than COPD
- 4) Any patient needing more than 6 litres per minute oxygen to correct desaturation
- 5) Severe desaturation: SaO2 < 80% during 6 Minute Walk Test
- 6) Any absolute contraindication to Pulmonary Rehabilitation

## 4.4 WITHDRAWAL CRITERIA

Standard clinical practice criteria for PR will be used, as per BTS PR guidelines.

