Baseline assessments prior to commencing PR will include symptom and quality of life assessments including Borg scale for assessment of breathlessness, Chronic Respiratory Questionnaire (CRQ), COPD Assessment Tool (CAT) and the Hospital Anxiety and Depression score (HAD); a 6MWT to measure exercise capacity and Handheld dynamometer to measure muscle strength. In addition we will measure activity at home during and after PR using pedometers as this has never been investigated previously. A yamax Digi-walker SW-200 pedometer will be used to count the number of steps taken per day. Patients will be instructed to wear the device on left side of the body all the time, except when sleeping or showering. Pedometer placement was standardised by placing it on the belt or waistband, in the midline of the thigh, consistent with the manufacturers recommendation and with other studies conducted previously (6, 7). Patients will be record daily step counts on daily diary cards until their final follow up. The subjects will be randomised to receive either oxygen at the flow rate determined at the initial assessment to a maximum flow rate of 6 litres per minute, or room air. The subjects will then undergo a standard program of PR over 6 – 8 weeks and then undergo reassessment. The measures of exercise capacity at the follow up assessment will be carried out off oxygen and will be carried out by an observer blinded as to whether they received oxygen or not during PR. All patients will be provided with ambulatory oxygen for domiciliary after completing PR. All patients will have repeat assessments at 8 and 12 weeks after completion of PR. At these visits data will also be collected on activity, number of exacerbations and hospitalisations and on-going usage of ambulatory oxygen.

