# 6. ASSESSMENT AND FOLLOW-UP

The subjects will attend for 2 additional visits at 2 months and 3 months after completing PR for follow-up assessments that will involve completing questionnaires and measurements of exercise capacity (6 Minute Walk Test).

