## **Definition of end of study**

All patients recruited to the study will have completed the study when they attend for the 3 month follow up assessments.

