#### 8.2 CONSENT

Consent to enter the study must be sought from each participant only after a full explanation has been given, an information leaflet offered and time allowed for consideration. Signed participant consent should be obtained. The right of the participant to refuse to participate without giving reasons must be respected. After the participant has entered the study the clinician remains free to give alternative treatment to that specified in the protocol at any stage if he/she feels it is in the participant's best interest, but the reasons for doing so should be

recorded. In these cases the participants remain within the study for the purposes of followup and data analysis. All participants are free to withdraw at any time from the protocol treatment without giving reasons and without prejudicing further treatment.

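### The 6MWTs after baseline are timed only from completion of PR, so patients who stop PR have no stated assessment date and the primary comparison may reduce to completers

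*Combined protocol and SAP*

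**What the plan says.** The visit schedule hangs on the PR programme. Section 3 says: "The subjects will then undergo a standard program of PR over 6 – 8 weeks and then undergo reassessment". It then says: "All patients will have repeat assessments at 8 and 12 weeks after completion of PR". Section 6 counts the later visits the same way, as "2 additional visits at 2 months and 3 months after completing PR for follow-up assessments". Appendix 1 heads its three post-baseline columns by completion of PR and by weeks after it. No 6MWT is dated from randomisation or from the start of the programme.

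On stopping, Section 4.4 says only: "Standard clinical practice criteria for PR will be used, as per BTS PR guidelines". Section 8.2 lets the clinician give a different treatment and adds: "In these cases the participants remain within the study for the purposes of followup and data analysis". It then says: "All participants are free to withdraw at any time from the protocol treatment without giving reasons". The end-of-study definition reads: "All patients recruited to the study will have completed the study when they attend for the 3 month follow up assessments".

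Section 3.1 makes the 6MWT the primary outcome. Section 7 lists a t test, ANOVA and correlation. It names no analysis population and no method for missing data, and it sets the minimum at 20 per group, equal to the calculated number.

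**The concern.** A patient who stops PR early may never have a completion date. If the schedule is followed literally, that patient then has no dated end-of-programme 6MWT and no dated follow-up 6MWT. A walk test that was not done cannot be recovered later.

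This matters more here than in most small trials. Everyone enrolled desaturates on exercise and has shown improvement with ambulatory oxygen, and one arm then trains on air. The trial's own hypothesis is that oxygen improves exercise capacity during PR. It is therefore plausible that stopping differs between arms and is commoner among weaker walkers. If so, those left with a 6MWT are no longer the two groups that randomisation made comparable.

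**Working it through.** **1. Which patients have a dated 6MWT**

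| Situation | Kept in the study? | Date for the next 6MWT? |
|---|---|---|
| Completes PR | Yes | Yes (Sections 3 and 6, Appendix 1) |
| Clinician gives another treatment, PR not completed | Yes (Section 8.2) | None stated |
| Patient withdraws from protocol treatment | Suggested by the wording of 8.2, not stated | None stated |
| Stops under Section 4.4 | Not stated | None stated |
| Randomised, never starts PR | Not stated | None stated |

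The pedometer diary is different. Patients record "daily step counts on daily diary cards until their final follow up", so the diary does not wait for completion of PR. The gap concerns the 6MWT and the other clinic assessments.

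**2. The plan's own sample size, to obtain a scale**

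The documents give no SD, so 20 and 29 per group cannot be derived from stated inputs. Reading the effect as a percentage of the mean, with two-sided 5% and 80% power:

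n = 2 × (1.96 + 0.842)² × (CV / effect)²

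With an assumed CV (SD/mean) of 0.335:
- 30% effect: 15.70 × (0.335/0.30)² = 19.6, so 20.
- 25% effect: 15.70 × (0.335/0.25)² = 28.2, so 29.

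Both figures are reproduced, but only with a back-solved CV. By the exact t test, 20 per group detects 0.909 SD with 80% power, which puts the CV at 0.30/0.909 = 0.33. Below, 1 SD is 33% of the mean and the planned effect is 0.91 SD.

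**3. Bias by simple algebra**

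Assume no true effect, a fraction p of an arm stopping, and stoppers walking D SD less than completers. The completers' mean is then pD above the mean of the whole arm. So:

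bias (oxygen − air) = D × (p_oxygen − p_air)

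With 10% and 30% stopping:
- D = 0.5: 0.5 × (−0.20) = −0.10 SD, or 3.3% of the mean.
- D = 1.0: 1.0 × (−0.20) = −0.20 SD, or 6.6% of the mean.

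With equal rates and the same D in both arms, the bias is zero.

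**4. Bias, type I error and power by simulation**

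Assumptions: 20 per arm, normal outcomes, a constant treatment effect, the chance of stopping rising as walking ability falls (logistic, slope 1 to 2 per SD), calibrated to the stated rates, and a two-sided t test on completers.

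| Stopping, air / oxygen | Bias against oxygen | Two-sided type I error | Power at 0.91 SD | Power if stopping is unrelated to walking |
|---|---|---|---|---|
| 30% / 10% | 0.16 to 0.23 SD | about 7 to 11% | about 54 to 57% | about 69% |
| 20% / 10% | 0.08 to 0.12 SD | about 5 to 7% | about 68 to 70% | about 72% |
| Equal rates | 0 | about 5% | not a bias question | – |

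As a share of the mean, 0.16 to 0.23 SD × 33% is about 5 to 8%, against the 30% target. As a share of the planned effect, 0.16/0.91 = 18% and 0.23/0.91 = 25%.

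At 30%/10%, all of the type I error above 5% lies in the direction of oxygen appearing worse. The chance of a false claim of benefit falls below its nominal 2.5%.

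**The case against.** A reader might infer that the protocol plans a completers' analysis, that Section 4.4 removes patients from the study, or that it contradicts Section 8.2. The documents support none of these.

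- No section excludes non-completers. Section 3 promises repeat assessments for all patients, the end-of-study definition speaks of all recruited patients, and Section 8.2 words the patient's withdrawal as withdrawal from protocol treatment. The intent leans towards retention.
- Section 4.4 relies on an outside guideline that cannot be checked here. It is silent on retention where 8.2 speaks. That calls for clarification, and it is not a contradiction.
- Completion could be read as the scheduled end of a standard programme, which exists for anyone who started. This is a fair reading, but the text does not adopt it. A programme of 6 to 8 weeks gives no single date, and a patient who never starts still has none.

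It would also go too far to say that the randomised comparison is broken. Bias needs stopping, or its reasons, to differ by arm and to relate to walking. The rates above are assumed, and the direction is an inference from the trial's hypothesis. Much of the power loss is also not bias. At 20%/10%, loss unrelated to walking already takes power from 80% to about 72%, and selection takes it only a little lower. That part belongs to the separate absence of a dropout allowance.

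What stands after all this is that retention without a visit date does not produce a 6MWT, and no sentence commits the analysis to all randomised patients.

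**Conclusion.** The concern holds in a limited form. The timing of every post-baseline 6MWT depends on completion of PR, stopping PR is not separated from leaving the study, and the analysis population is not stated. The primary comparison may therefore reduce to completers, although the protocol does not say that it will.

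If it did, and if 30% of air and 10% of oxygen patients stopped, the bias would be 0.16 to 0.23 SD against oxygen. A milder imbalance of 20% and 10% gives about half that, and no imbalance gives none. The likely harm is a missed or understated benefit, not a false claim of one. These sizes rest on assumed rates, an assumed link with walking ability and a back-solved CV. The gap itself rests on the text alone. It should be closed before recruitment, because walk tests not done cannot be added later.

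**What to change.** - **Sections 4.4 and 8.2:** state that stopping PR, for any reason, is not withdrawal from the study, and that follow-up continues unless the patient withdraws consent to it. Leave the clinical criteria for stopping PR as they are.
- **Sections 3 and 6, Appendix 1:** assess every randomised patient who still consents at a fixed time from randomisation, with a window that fits the 6 to 8 week programme, whether or not PR was started or completed. Time the 8- and 12-week visits from that date. An anchor at the start of PR would still miss patients who never begin.
- **Section 7:** analyse all patients in the arm to which they were randomised. Report non-completion of PR and missing 6MWTs by arm, with reasons. Add a sensitivity analysis for missing 6MWTs that lets the missing values differ from the observed ones, separately by arm, and say how patients who have died or cannot walk enter it.

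The cost is wording in six places and the recall of patients who stopped: at the assumed rates, 20 × 0.10 = 2 to 20 × 0.30 = 6 per arm. Some completers will be tested a little after their last session, which the window should limit. No extra patients or procedures are needed. The loss of power from missing patients is a sample-size matter that this change reduces but does not remove.

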#### 5. ADVERSE EVENTS

#### 5.1 **DEFINITIONS**

Adverse Event (AE): any untoward medical occurrence in a patient or clinical study subject.

**Serious Adverse Event (SAE):** any untoward and unexpected medical occurrence or effect that:

- Results in death
- **Is life-threatening** refers to an event in which the subject was at risk of death at the time of the event; it does not refer to an event which hypothetically might have caused death if it were more severe
- Requires hospitalisation, or prolongation of existing inpatients' hospitalisation
- Results in persistent or significant disability or incapacity
- Is a congenital anomaly or birth defect

Medical judgement should be exercised in deciding whether an AE is serious in other situations. Important AEs that are not immediately life-threatening or do not result in death or hospitalisation but may jeopardise the subject or may require intervention to prevent one of the other outcomes listed in the definition above, should also be considered serious.

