#### 5.3 REPORTING PROCEDURES

All adverse events should be reported. Depending on the nature of the event the reporting procedures below should be followed. Any questions concerning adverse event reporting should be directed to the Chief Investigator in the first instance.

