#### 5.3.1 Non serious AEs

All such events, whether expected or not, should be recorded.

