#### 5.3.2 Serious AEs

An SAE form should be completed and faxed to the Chief Investigator within 24 hours. However, relapse and death due to COPD Exacerbation and hospitalisations for elective treatment of a pre-existing condition do not need reporting as SAEs.

All SAEs should be reported to the JRCO, Imperial College healthcare NHS trust where in the opinion of the Chief Investigator, the event was:

- 'related', ie resulted from the administration of any of the research procedures;
   and
- 'unexpected', ie an event that is not listed in the protocol as an expected occurrence

Reports of related and unexpected SAEs should be submitted within 15 days of the Chief Investigator becoming aware of the event, using the NRES SAE form for non-IMP studies. The Chief Investigator must also notify the Sponsor of all SAEs.

Local investigators should report any SAEs as required by their Local Research Ethics Committee, Sponsor and/or Research & Development Office.

Contact details for reporting SAEs
[contact] Attention Joint Research compliance office
Please send SAE forms to: [name]
[contact] (Mon to Fri 09.00 – 17.00)

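### The SAE definition in 5.1 requires unexpectedness, which conflicts with 5.3.2 and leaves a serious but expected event with no specific reporting route

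*Combined protocol and SAP*

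**What the plan says.** Section 5.1 defines an adverse event with no reference to expectedness: "any untoward medical occurrence in a patient or clinical study subject". The SAE definition adds a condition. An SAE is "any untoward and unexpected medical occurrence or effect that" meets one of five criteria: death, threat to life, new or prolonged hospital stay, lasting disability, or congenital anomaly. A medical-judgement clause then says that other important events "should also be considered serious", again without asking whether they were expected.

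Section 5.3 opens with a general rule, "All adverse events should be reported", and refers the reader to the procedures that follow. For non-serious events, 5.3.1 says "All such events, whether expected or not, should be recorded".

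Section 5.3.2 attaches three duties to SAEs:
- "An SAE form should be completed and faxed to the Chief Investigator within 24 hours".
- "The Chief Investigator must also notify the Sponsor of all SAEs".
- SAEs that the Chief Investigator considers both related and unexpected are reported to the JRCO within 15 days. The second term is explained as "unexpected', ie an event that is not listed in the protocol as an expected occurrence".

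The same section exempts COPD relapse, deaths from a COPD exacerbation, and planned admissions to treat an existing condition from SAE reporting.

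**The concern.** Whether an event is serious and whether it was expected are separate questions. Seriousness normally decides whether an event is notified promptly. Expectedness normally decides which of the notified events go on to a further, expedited report. Section 5.3.2 is built that way, but 5.1 puts expectedness into the definition itself.

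The effect falls on serious events that someone regards as foreseeable in patients with COPD. By the letter of 5.1 these are not SAEs, so the 24-hour form and the notice to the sponsor do not apply. Nor do they reach the point at which the Chief Investigator gives an opinion on relatedness for the JRCO. At stake is the completeness and speed of safety oversight: a sponsor who receives all SAEs would not necessarily be receiving all serious events. The primary outcome, the sample size and the efficacy analysis are not affected.

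**Working it through.** No arithmetic applies, and the plan gives no figure to reproduce. The check takes the wording of 5.1, 5.3, 5.3.1 and 5.3.2 and applies it to each combination of seriousness and expectedness, leaving aside events that 5.3.2 exempts by name.

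**Step 1: routes under the literal text.**

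| Event | Status under 5.1 | Specific route |
|---|---|---|
| Non-serious, expected | AE | Recorded under 5.3.1 |
| Non-serious, unexpected | AE | Recorded under 5.3.1 |
| Serious, unexpected | SAE | 24-hour form and notice to sponsor; also the JRCO within 15 days if related |
| Serious, expected | AE, but not an SAE | None: 5.3.1 covers non-serious events, and the duties in 5.3.2 are tied to SAEs |

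The last row is the gap. Only the opening sentence of 5.3 reaches it, and that sentence sets no form, deadline or recipient.

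**Step 2: which section is out of line?** Four features suggest that the two words in 5.1 are the anomaly.
1. If every SAE is already unexpected, the unexpectedness test for the JRCO report removes nothing. It does work only if some SAEs are expected.
2. The named exemption in 5.3.2 covers events that are foreseeable in this population. It would be largely unnecessary if expected events already lay outside the definition.
3. The medical-judgement clause has no expectedness condition. Read literally, an important event that led to neither death nor hospital admission can count as serious, while an expected admission is not an SAE.
4. Non-serious events are to be recorded regardless of expectedness, but nothing equivalent is said for serious ones. The graver class therefore has the weaker rule.

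**Step 3: what does unexpected mean?** The only definition is in 5.3.2 and points to a list. No list of expected occurrences appears in the protocol. (Numbering runs from 5.1 to 5.3 in both the contents and the body; that does not show a list was ever there.) Three readings are open:
- *List test, with no list.* Virtually every serious event is unexpected. The gap is then almost empty, but the JRCO filter reduces to relatedness alone.
- *The exemption treated as the list.* The events left out are those that 5.3.2 already excuses, so 5.1 adds nothing.
- *Clinical or everyday sense.* Serious events common in COPD may be called expected, and those outside the exemption fall into the gap.

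The text does not say which reading governs 5.1, so the size of the gap cannot be fixed.

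**The case against.** The strongest reply is that the gap is nearly empty on the protocol's own terms. Unexpected is defined once, by a list. With no list, almost nothing is expected, so almost every serious event is an SAE and gets the form and the notice. This stands as a limit on size. It does not remove the conflict, because 5.1 does not refer to that definition and the filter in 5.3.2 is left without function.

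Three further points also stand in part.
- **The exemption.** COPD relapse, deaths from exacerbation and planned admissions are excused by a separate sentence. Their absence from SAE reporting does not depend on 5.1, and deleting two words there would not bring them back. Whether relapse includes an admission for exacerbation is not stated.
- **Backstops.** All adverse events are to be reported, and questions go to the Chief Investigator. A serious expected event therefore does not escape reporting altogether; it loses the prompt, defined route.
- **Separate collection.** Section 3 collects the number of hospitalisations from all patients at the visits 8 and 12 weeks after rehabilitation, whatever their SAE status. This protects the later count of admissions, although the look-back period is not stated and such a count brings neither prompt notice nor a judgement of cause.

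A reader might go further and infer that the comparison of serious events between arms turns on how each site reads one word, or that most respiratory admissions would go unreported. The documents support neither inference. Hospitalisations are collected independently, some respiratory events are exempt for another reason, and recruitment is from the hospital sites of one Trust, with the Chief Investigator coordinating the study and receiving the SAE forms. Nothing shows that sites would read the word differently.

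**Conclusion.** The point holds as a conflict between 5.1 and 5.3.2. Taken literally, a serious event that is judged expected and is not exempt by name has no 24-hour form and no notice to the sponsor. This rests on the wording alone and needs no assumption about event rates.

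Its practical size is unknown. The documents give no admission rate, no list of expected events, and no statement of which sense of unexpected applies in 5.1. The number affected may be few. It would be wrong to attach a percentage of unreported events to this wording, or to present it as a bias between arms. It is a drafting fault in safety reporting that is worth correcting because the correction is simple.

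**What to change.** 1. In 5.1, delete the words *and unexpected* from the SAE definition, so that seriousness alone defines an SAE and triggers the 24-hour form and the notice to the sponsor.
2. In 5.3.2, keep expectedness only as the filter, with relatedness, for the 15-day report to the JRCO.
3. Add the list of expected occurrences to which that filter refers, and reconcile it with the existing exemption for COPD exacerbation and elective hospitalisation. State whether the exempted events are expected SAEs or are outside SAE reporting altogether, and what relapse covers.

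The cost is two words removed, a short list and a sentence of clarification. The downside is a few more SAE forms in a trial planned for at least 40 patients (2 × 20). No outcome, visit or analysis changes.
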